### 8.8.3 Drug interactions

In vitro studies demonstrate that IL-6 reduces cytochrome CYP1A2, CYP2C9, CYP2C19, and CYP3A4 enzyme expression. Caution should be exercised in patients who will start sarilumab treatment while on therapy with CYP3A substrates (e.g. oral contraceptives or statins).

Sarilumab or tocilizumab, which antagonize IL-6, may normalize the formation of CYP450 enzymes. As a result, the therapeutic effect of drugs that are metabolized by these CYP450 isoforms may decrease when RA patients start receiving sarilumab. CYP450 substrates with a narrow therapeutic index should be monitored in patients that enter the treatment period. Some examples of CYP450 substrates with a narrow therapeutic index that require therapeutic monitoring (pharmacodynamics and/or drug concentration) include: warfarin, cyclosporine, theophylline, digoxin, antiepileptics like carbamazepine (Carbatrol®, Tegretol®), divalproex (Depakote®), phenytoin (Dilantin®), or valproic acid (Depakene®); or antiarrhythmics, like disopyramide (Norpace®), procainamide (Procan®, Pronestyl®), or quinidine (Quinidex®, Quin-Release Quin-G®).

## 9 ASSESSMENT OF INVESTIGATIONAL MEDICINAL PRODUCT

### 9.1 PRIMARY ENDPOINT

- Change in the total RAID score from baseline to Week24.

The Rheumatoid Arthritis Impact of Disease (RAID) is a patient-reported outcome measure evaluating the impact of RA on patient quality of life which comprises 7 domains: pain, function, fatigue, physical and psychological wellbeing, sleep disturbance and coping.

Each domain is evaluated using a single question answered by a 0 to 10 numerical rating scale. Each domain also has a specific weight assigned by a patient survey. The RAID score is a continuous variable ranging from 0 (best) to 10 (worst) (see Appendix B).

The RAID score will be assessed at each assessment visit over the treatment period, from V2 (at first IMP administration) to V5 (at Week 24).

### 9.2 SECONDARY ENDPOINTS

#### 9.2.1 Secondary efficacy endpoints (6-month core period)

##### ***9.2.1.1 Values at each assessment visit and changes from baseline for the total RAID score, HADS, MATHys, FACIT-Fatigue, HAQ-DI, morning stiffness, International Physical Activity Questionnaire, and patient global assessment of disease activity***

All the studied PROs will be assessed at each visit over the treatment period (from V2 to V5). Questionnaires used are all valid and self-rating reliable scales.

The **Hospital Anxiety and Depression Scale (HADS)** measures anxiety and depression in both hospital and community settings. This questionnaire comprises 14 items divided into two subscales: anxiety and depression (see Appendix B). Each item is answered by a 0 to 3 rating scale, leading to maximum scores of 21 points for anxiety and depression. A total score up to 19 indicates a major depressive episode; a total score up to 13 indicates adjustment disorders and minor depression.

The **Multidimensional Assessment of Thymic States (MATHys)** is a multi-dimensional assisted self-administered questionnaire comprising five dimensions (emotional reactivity, cognition speed, psychomotor function, motivation and sensory perception) divided into 20 items relating to individual states as perceived by patients for the preceding week (see Appendix B). Each item is set out as a continuous measure in the form of a visual analogic scale of 10 cm on which the subject is asked to make a mark to indicate where he/she is positioned between the two predefined extreme propositions.

The **Functional Assessment of Chronic Illness Therapy – Fatigue (FACIT-F)** is a symptom-specific scale that measures fatigue in patients assess with chronic illness therapy over the 7 preceding days. This scale comprises 13 items scored on a 5-point Likert scale, from 0 (not at all) to 4 (very much) (see Appendix B). The figures are reversed during score calculations, so that higher score values indicate more favorable conditions. Total scores then range from 0 to 52, with lower scores representing greater fatigue.

The **Stanford Health Assessment Questionnaire Disability Index (HAQ-DI)** is a patient-oriented outcome assessment questionnaire specifically developed to assess the extent of a RA patient's functional ability. It consists of 20 questions referring to eight component sets: dressing/grooming, arising, eating, walking, hygiene, reach, grip, and activities (see Appendix B). Knowing that here are 2 or 3 questions for each section, scoring within each section is from 0 (without any difficulty) to 3 (unable to do). The eight category scores are averaged into an overall HAQ-DI score on a scale from zero (no disability) to three (completely disabled). It is not truly continuous but has 25 possible values.

The **duration of morning stiffness** (in minutes) will be self-reported by RA patients.

The **International Physical Activity Questionnaire (IPAQ)** is a 27-item self-reported questionnaire designed to measure physical activity of patient. It comprises several parts (job-related, transport-related, domestic and leisure-time physical activity) and intensities (moderate, vigorous, walking) and includes sitting time (see Appendix B). Based on frequency, duration and intensity of self-reported physical activity, individuals are categorized into low, moderate and high physical activity groups.

The **patient global assessment of disease activity** measures RA activity as perceived by the patient, using a 100 mm horizontal visual analog scale (VAS).

#### **9.2.1.2 Values at each assessment visit and changes from baseline for ESR, DAS28-ESR, CDAI, and joint counts (TJC, SJC)**

At each visit, all the efficacy parameters will be assessed.

The **erythrocyte sedimentation rate (ESR)** is measured in mm/hr. This laboratory test will be performed in a local medical laboratory.

The DAS28 is a combined index for measuring disease activity in RA. The index includes the assessment of 28 joints for swelling and tenderness, acute phase response (ESR or CRP), and general health status. For this study, ESR will be used to calculate the DAS28 score. The index is calculated using the following formula:

$$\mathbf{DAS28-ESR} = 0.56 \times \sqrt{(TJC28)} + 0.28 \times \sqrt{(SJC28)} + 0.70 \times \ln(ESR) + 0.014 \times PtGA$$

where **TJC28** is the tender joint count on 28 joints, **SJC28** is the swollen joint count on 28 joints,  $\ln$  is the natural log, ESR is the erythrocyte sedimentation rate (mm/hour), i.e., patient's global assessment of disease activity (PtGA using a 100 mm VAS). The 28 joints to be assessed are detailed in Appendix B.

The DAS28 scale ranges from 0 to 10, where higher scores represent higher disease activity.

The **CDAI** is a combined index for measuring disease activity in RA that does not include a laboratory test. It is calculated as follows:

$$\text{CDAI} = \text{TJC28} + \text{SJC28} + \text{PtGA (in cm)} + \text{PhGA (in cm)}$$

where TJC28 is the tender joint count on 28 joints, SJC28 is the swollen joint count on 28 joints, PtGA is patient's global assessment of disease activity (100mm VAS), and PhGA is the physician's global assessment of disease activity (100mm VAS). The 28 joints to be assessed are detailed in Appendix B.

### **9.2.1.3 DAS28-ESR Low Disease Activity (LDA) and remission, CDAI LDA and remission, at W12 and W24**

A DAS28-ESR score of <2.6 represents clinical remission and a score of  $\leq 3.2$  represents low disease activity.

A CDAI score of  $\leq 2.8$  represents clinical remission and a score of  $\leq 10.0$  represents low disease activity.

For both indexes, clinical remission is included in low disease activity.

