
ENDPOINTS
	
Primary endpoint (6-month core period):
 
Change in the total RAID score from baseline to Week24
 
Secondary efficacy endpoints (6-month core period):
 
 
• Values at each assessment visit and changes from baseline for the total RAID score, HADS, MATHys, FACIT-Fatigue, HAQ-DI, morning stiffness, International Physical Activity Questionnaire, and patient global assessment of disease activity
 
• Values at each assessment visit and changes from baseline for ESR, DAS28-ESR, CDAI, and joint counts (TJC, SJC)
 
• DAS28-ESR Low Disease Activity (LDA) and remission, CDAI LDA and remission, at W12 and W24
 
 
Safety endpoints (6-month core and long-term extension periods):
 
 
• Incidence and severity of adverse events (AEs), serious and non-serious AEs, AESIs, AEs leading to dose modification or treatment withdrawal, AEs leading to death
 
• Physical examination, vital signs, and clinically significant laboratory abnormalities over time.
 

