### 5.2 SECONDARY (6-MONTH CORE PERIOD)

- To assess the change of the RAID score from baseline (to W4, W12, and W24) in patients with moderately to severely active RA and inadequate response or intolerance to current csDMARD or TNF inhibitors, treated with sarilumab in combination with csDMARD and/or monotherapy.
- To assess the effect of sarilumab in combination with csDMARD and/or monotherapy on other patient-reported outcomes (global assessment of disease activity, disability, morning stiffness, fatigue, anxiety/ depression, mood disorders, and physical activities), in patients with moderately to severely active RA and inadequate response or intolerance to current csDMARD or TNF inhibitors.
- To assess the efficacy of sarilumab in combination with csDMARD and/or monotherapy using DAS28-ESR and CDAI in patients with moderately to severely active RA and inadequate response or intolerance to current csDMARD or TNF inhibitors.
- To assess the safety of sarilumab in combination with csDMARD and/or monotherapy in patients with moderately to severely active RA and inadequate response or intolerance to current csDMARD or TNF inhibitors.

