## 6 STUDY DESIGN

### 6.1 DESCRIPTION OF THE STUDY

This is a national, multicenter, open-label, single-arm phase IV study designed to assess the effect of sarilumab on patient-reported impact of disease, using the rheumatoid arthritis impact of disease (RAID) questionnaire, in patients with moderately to severely active RA and inadequate response or intolerance to current csDMARD or TNF inhibitors.

Four study periods are defined for this study:

- Screening period: within 28 days prior to study treatment start (Baseline visit, Day 1), out-patient eligibility is determined at the Screening visit. At Baseline visit, patient's inclusion in the study will be established.
- 6-month core period: patients who fulfil the enrolment criteria will start the investigational medicinal product (IMP), SC injection of sarilumab 200 mg every 2 weeks as monotherapy and/or in combination with methotrexate (MTX) or other csDMARD (at investigator's discretion) for 24 weeks. Patient visits are scheduled at Baseline, W4, W12, and W24.
- Long-term extension period: all patients who will complete the 6-month-core-period will be allowed to continue the treatment with sarilumab, every 2 weeks for a maximum of another 24 weeks or until the commercial availability of sarilumab, depending whichever comes first. Patient visits are scheduled every 12 weeks over the LTE period (at W36 and W48).
- Post-treatment follow-up: each patient will have one follow-up visit, between 2 and 4 weeks after his/her last administration of sarilumab.

Around 140 patients enrolled in 35 university hospital and general hospital centers are expected throughout mainland France.

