## 7 SELECTION OF PATIENTS

### 7.1 INCLUSION CRITERIA (6-MONTH CORE PERIOD)

- I 01. Patient with moderately to severely active RA according to the 2010 EULAR/ACR criteria (see Appendix A)
- I 02. Patient with moderate to severe disease activity defined as a DAS28-ESR >3.2 at Screening
- I 03. Patient with inadequate response within at least the last 3 months or intolerance to current csDMARD or to at least one anti-TNF therapy (as defined by the investigator)
- I 04. Oral corticosteroids ( $\leq 15$  mg/day prednisone or equivalent) and non-steroidal anti-inflammatory drugs (NSAID) and cyclo-oxygenase-2 inhibitors (COX-2) (up to the maximum recommended dose) are allowed if at a stable dose for at least 4 weeks prior to Baseline
- I 05. Permitted csDMARDs are allowed if at a stable dose for at least 4 weeks prior to Baseline
- I 06. Patient able and willing to give written informed consent and to comply with the requirements of the study protocol.

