### **7.2.2 Exclusion criteria related to the current knowledge of Sanofi compound**

- E 11. Pregnant or breastfeeding woman
- E 12. Women of childbearing potential not protected by highly-effective contraceptive method(s) of birth control (as defined in the informed consent form and/or in a local protocol addendum/amendment) over the study period and for at least 3 months following the last dose of sarilumab, and/or who are unwilling or unable to be tested for pregnancy
- E 13. History of severe allergic or anaphylactic reactions to human, humanized, or murine monoclonal antibodies (or to any of the excipients associated to sarilumab)
- E 14. Immunization with a live/attenuated vaccine within 4 weeks prior to Baseline
- E 15. Stage III or IV cardiac failure according to the New York Heart Association classification
- E 16. History of previous gastrointestinal perforation or diverticulitis
- E 17. Known active current/ recurrent infections (including but not limited to active tuberculosis [TB] or history of incompletely treated TB and atypical mycobacterial disease, hepatitis B and C, and herpes zoster)  
  
NOTE: in case of latent TB infection the patient may be included if a subsequent appropriate anti TB treatment is initiated since at least 3 weeks
- E 18. Positive hepatitis B surface antigen (HbsAg), and/or positive total hepatitis B core antibody, and/or positive hepatitis C antibody (HCV) at the Screening visit
- E 19. Evidence of serious uncontrolled concomitant disease, including severe uncontrolled hypercholesterolemia or hypertriglyceridemia
- E 20. Patients with any of the following laboratory abnormalities at the Screening or Baseline visit:

- Hemoglobin <8.5 g/dL
- White blood cells <3000/mm^3
- Absolute neutrophil count <2000/mm^3
- Absolute lymphocyte count <500/mm^3
- Platelet count <150 000 cells/mm^3
- Creatinine clearance <30 mL/min
- AST or ALT >1.5 x ULN.
- Bilirubin (total) >ULN, unless Gilbert's disease has been determined by genetic testing and has been documented
- Total fasting cholesterol >3.50 g/L [9.1 mmol/L]) or triglycerides >5.00 g/L [5.6 mmol/L])

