### **11.4.2.3 Multiplicity considerations**

Not applicable: all analyses are descriptive without test.

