5.1.3. Secondary endpoints (6-month core period)

- **PROs questionnaires**

- [RAID](#) score per item and total score^{DD}
The RAID score gives a number between 0 and 10. A higher score on the RAID indicates more impact of the disease.
A score ≤ 2 out of 10 is considered a patient-acceptable status.

- Hospital Anxiety and Depression Scale ([HADS](#)):
 - Per item
 - Anxiety calculated score as quantitative^{DD} and in classes
 - Normal (0-7)
 - Borderline abnormal (8-10)
 - Abnormal (11-21)
 - Depression calculated score as quantitative^{DD} and in classes:
 - Normal (0-7)
 - Borderline abnormal (8-10)
 - Abnormal (11-21)
- Multidimensional Assessment of Thymic States ([MATHys](#))^{DD}
 - Per item
 - 5-dimension scores:
 - Emotion
 - Cognition
 - Psychomotor function
 - Motivation
 - Sensory perception
 - MATHys total score
- Functional Assessment of Chronic Illness Therapy – Fatigue ([FACIT-F](#)) per item and total score
- Health Assessment Questionnaire - Disability Index ([HAQ-DI](#)) per domain (dressing & grooming, arising, eating, walking, hygiene, reach, grip and activities) and total score.
- International Physical Activity Questionnaire ([IPAQ](#)) classification per domain and total score as quantitative and in classes:
 - Low physical activity
 - Moderate physical activity
 - High physical activity
- Patient global assessment of disease activity using a 100 mm Visual Analogue Scale (VAS)
- Duration of morning stiffness (minutes)
- **Evaluation of RA activity**
- Erythrocyte sedimentation rate (ESR) (1st hour) (mm/h)
- Number of swollen joints (SJC)
- Number of tender joints (TJC)
- DAS28-ESR^{DD}
 - Low Disease Activity (LDA) (Yes/No)
 - Remission (Yes/No)
- CDAI^{DD}
 - Low Disease Activity (LDA) (Yes/No)
 - Remission (Yes/No)

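### DAS28-ESR and CDAI low disease activity at W12 and W24 cannot be read as improvement unless LDA status at baseline (V2) is shown beside them

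*Protocol*

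**What the plan says.** **Entry.** I 02 in Protocol 7.1 reads: "Patient with moderate to severe disease activity defined as a DAS28-ESR >3.2 at Screening". The flow chart (Protocol 1.2) and Protocol 10.1.2 have DAS28-ESR and CDAI measured again at V2, up to 28 days later. I 02 stays tied to Screening. By contrast, E 20 in Protocol 7.2.2 covers "Patients with any of the following laboratory abnormalities at the Screening or Baseline visit". No criterion refers to CDAI.

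**Endpoint.** The Protocol summary lists "DAS28-ESR Low Disease Activity (LDA) and remission, CDAI LDA and remission, at W12 and W24". Protocol 9.2.1.3 states "A DAS28-ESR score of <2.6 represents clinical remission and a score of" 3.2 or less is LDA. For CDAI the limits are 2.8 or less for remission and 10.0 or less for LDA. Remission counts within LDA for both indices. SAP 5.1.3 carries the item only as "Low Disease Activity (LDA) (Yes/No"), for each index.

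**Use.** The objective in Protocol 5.2 is "To assess the efficacy of sarilumab in combination with csDMARD and/or monotherapy using DAS28-ESR and CDAI". Protocol 6.1 describes the design: "This is a national, multicenter, open-label, single-arm phase IV study". On multiplicity, Protocol 11.4.2.3 says "Not applicable: all analyses are descriptive without test".

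**Baseline status elsewhere.** SAP Appendix B cross-classifies baseline class against visit class for RAID, HADS, HAQ-DI and IPAQ, which separates improvement from an unchanged good state. It has no such table for DAS28-ESR or CDAI.

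**The concern.** LDA at 3.2 or less is the complement of the entry rule, and entry rests on one reading. A patient who screens just above 3.2 can read below it at V2 with no change in the disease. The CDAI case needs no measurement error, because the entry rule does not constrain CDAI.

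With a control arm, such patients would appear on both sides and largely cancel. Here they stay in the numerator. A reader who sees the W24 LDA percentage under an efficacy objective will naturally take it as the share who reached LDA on treatment. Without V2 status, nobody can tell how much of it was there before the first dose.

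**Working it through.** The documents state no expected LDA rate, and no mean, SD or reliability for DAS28-ESR, so there is no planned figure to reproduce.

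**1. A patient eligible on DAS28-ESR and already in CDAI LDA.** Take TJC 1, SJC 1, ESR 40 mm/h, PtGA 40 mm, PhGA 30 mm, with the formulas in Protocol 9.2.1.2.

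- DAS28-ESR = 0.56×√1 + 0.28×√1 + 0.70×ln(40) + 0.014×40 = 0.56 + 0.28 + 2.58 + 0.56 = 3.98, above 3.2, so I 02 is met.
- CDAI = 1 + 1 + 4 + 3 = 9, not above 10, so already LDA.
- The classification criteria in Protocol Appendix B can also be met. One to three small joints (2), high-positive serology (3) and symptoms for six weeks or more (1) give 6, the threshold, even if the ESR is scored as normal.

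If nothing changes, this patient counts as CDAI LDA at W12 and at W24.

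**2. DAS28-ESR LDA with no true change.** Assume a constant true level, Normal with mean μ and between-patient SD sb, plus independent visit noise with SD sw. Keep patients with Screening above 3.2. With z = (3.2 − μ)/√(sb² + sw²) and ρ = sb²/(sb² + sw²),

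P(W24 ≤ 3.2 given Screening > 3.2) = [Φ(z) − Φ₂(z, z; ρ)] / [1 − Φ(z)].

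For μ = 5.0, sb = 1.0, sw = 0.6: z = −1.8/√1.36 = −1.543 and ρ = 1/1.36 = 0.735. The result is (0.0614 − 0.0273)/0.9386 = 3.6%.

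Over sb 1.0–1.2 (simulation):

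| μ before selection | Enrolled mean at Screening | LDA at W24, sw 0.6 | LDA at W24, sw 0.4–0.8 |
|---|---|---|---|
| 4.2 | about 4.5–4.8 | 10.0% | 6.6–13% |
| 4.6 | about 4.9 | 6.3–6.9% | 4–9% |
| 5.0 | about 5.1–5.3 | 3.6–4.4% | 2–6% |
| 5.5 | about 5.6 | 1.6–2.3% | 1–4% |
| 6.5 | about 6.5 | under 1% | under 1% |

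V2 and W24 have the same distribution in this model, so the same share is already in LDA at V2. A V2 row therefore shows the size of the problem directly, from the trial's own data.

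**3. What each addition does** (μ 4.2, sw 0.6; 10.0% as planned).

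- LDA at W24 among patients above 3.2 at V2: 6.5–6.9%.
- LDA at both W12 and W24, no V2 restriction: 3.8–4.1%.
- Both conditions: 2.0%.

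The V2 restriction removes patients already in LDA. It does not remove crossings due to noise after V2.

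**4. The two formulas.** SAP Appendix A item 2 has ln(ESR) without the 0.70 given in Protocol 9.2.1.2. The SAP score is higher by 0.30×ln(ESR): 0.48, 0.69, 0.90 and 1.11 at ESR 5, 10, 20 and 40. The patient in step 1 would score 3.98 + 1.11 = 5.09. If Screening used one formula and W12/W24 the other, the cut-offs would no longer be complementary and later LDA would be lower.

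**The case against.** **LDA is a state, not a response.** Neither document speaks of LDA achieved, and nothing is tested. This stands. It is why the all-patient percentage should remain and why the point is limited to how it may be read.

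**V2 status may already be planned.** SAP 5.3.2.3 promises values at each assessment visit over the treatment period for each secondary endpoint, and Protocol 9.2.1.1 describes that period, for the PROs, as running from V2 to V5. On that reading LDA at V2 will appear. But the SAP sentence goes on to speak of PRO total scores, and the Protocol names only W12 and W24 for LDA. The reading is possible, not secure, so an explicit statement is needed.

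**The change measures are sound.** Change in DAS28-ESR and CDAI is computed from V2 (SAP Appendix A item 6), not from the Screening value used for selection. A reader might infer that the efficacy objective as a whole is overstated. The documents do not support that: continuous changes, joint counts and the stricter remission category serve the same objective.

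**The size may be trivial.** A reader might take 10% as the expected inflation. That needs an enrolled mean near 4.6–4.7, which the documents do not give. What indirect evidence they offer points higher: the monotherapy trial in Protocol 4.1.2 had a mean DAS28-ESR change of −3.28 with 26.6% in remission, and the sample-size table in Protocol 11.1 highlights a baseline RAID of 6.5. Still, I 02 admits anyone above 3.2, so a milder population cannot be ruled out.

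**CDAI rests on one constructed patient.** True. It shows that the case is possible, not how common it is.

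**Conclusion.** The point holds as one of interpretation. Patients can be in DAS28-ESR or CDAI LDA at V2. The trial has no control arm, and the SAP does not clearly show baseline LDA status. The W12 and W24 percentages therefore cannot be read as improvement on treatment as they stand.

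The size is not known from the documents. With assumed SDs of 1.0–1.2 between patients and 0.4–0.8 between visits, and a constant true level, the no-effect DAS28-ESR share is about 7–13% for enrolled Screening means of about 4.5–4.8, about 2–6% near 5.1–5.3 and under 1% near 6.5. No figure can be given for CDAI.

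A reader might go further and conclude that the LDA definition is invalid, or that it must require confirmation or a minimum fall. The documents do not support this: the endpoint is a secondary, descriptive state, and no trial decision turns on it. Nor would showing V2 status replace a control arm. It would separate patients who changed from those who did not, without attributing the change to sarilumab.

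**What to change.** Before the LDA tables are produced:

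1. Reconcile the DAS28-ESR formula between Protocol 9.2.1.2 and SAP Appendix A item 2, and use one formula at every visit.
2. In SAP 5.1.3 and 5.3.2.3, state that DAS28-ESR and CDAI LDA and remission are tabulated at V2 beside W12 and W24.
3. In SAP Appendix B, add a baseline-by-visit decision table for each index, on the pattern of those for RAID and HADS. From it, report LDA at W12 and W24 among patients not in LDA at V2 (DAS28-ESR above 3.2; CDAI above 10).
4. Keep the all-patient percentage, labelled as the disease-state figure.

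LDA at both W12 and W24 is an optional extra. It would need the V2 restriction as well, otherwise patients in LDA from the start would count as confirmed. It would also leave out patients who first reach LDA between W12 and W24.

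The cost is SAP wording and one extra table per index, from data already collected. Eligibility and visits are unchanged. The restricted figure will have a smaller denominator and possibly a lower percentage.
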